### **6.3. Lifestyle and/or Dietary Requirements**

Throughout the study, subjects may undergo medical assessments and review of compliance with requirements before continuing in the study.

#### **6.3.1. Meals and Dietary Restrictions**

Subjects will fast overnight for at least 8 hours before dosing (water is permitted). Standard meals will be provided at all other times while subjects are resident at the CRU, as per the CRU's policy.

### ***6.3.2. Caffeine, Alcohol, and Tobacco***

Subjects will not consume caffeinated beverages (decaffeinated beverages are permitted) while at the CRU, and for 12 hours prior to admission to the CRU. At other times during the outpatient period, subjects will be allowed to maintain their regular caffeine consumption.

Alcohol consumption is not permitted while at the CRU, and for 12 hours prior to each study visit. At other times, alcohol consumption should be limited to 2 units per day (1 unit = 12 oz or 360 mL of beer; 5 oz or 150 mL of wine; 1.5 oz or 45 mL of distilled spirits).

Subjects who smoke will be advised to not increase their consumption of tobacco products during the study. Subjects will be asked to refrain from smoking for approximately 1 hour prior to each ECG and vital sign measurements, and to abide by the CRU smoking guidelines.

### ***6.3.3. Activity***

Subjects will be advised to maintain their regular levels of physical activity/exercise during the study, but to refrain from strenuous activity from 24 hours prior to each visit and 48 hours prior to any visit where creatine phosphokinase testing will occur (Day -1, Day 8, and Day 29). While certain study procedures are in progress at the site, subjects may be required to remain recumbent or sitting.

### ***6.3.4. Blood and Plasma Donation***

Subjects will not donate blood or plasma for 12 weeks following dosing with the study drug.

## **6.4. Screen Failures**

Individuals who do not meet the criteria for participation in this study (screen failure) may not be re-screened.

## 7. Dosing Regimens

### 7.1. Dosing Regimens Administered

This study will evaluate the PK, safety and tolerability of, and pain associated with 250-mg SC doses administered using 2 x 1-mL PFSs or an investigational 1 x 2-mL AI at 3 different injection sites.

Using the investigational 2-mL AI, the targeted injection duration will be approximately 5 seconds. Manual injections using the PFS should target an injection duration of about 5 to 10 seconds for each 1-mL injection to approximate the injection time range for the AI. The second of the 2 PFS injections should be administered 20 ( $\pm 2$ ) minutes after the first injection to allow for collection of 3 VAS pain score time points prior to administration of the second injection. Approximate injection durations for AIs and PFSs will be obtained using a calibrated stopwatch and recorded in the electronic case report form (eCRF).

Drug and device accountability records will be maintained by the site pharmacy.

Table AMAR.2 shows the dosing regimens for the study.

**Table AMAR.2. Dosing Regimens Administered**

Dosing Regimen		PFS			AI		
Reference/test	Reference 1	Reference 2	Reference 3	Test 1	Test 2	Test 3	
Injection site	Arm	Thigh	Abdomen	Arm	Thigh	Abdomen	
Product	LY3074828			LY3074828			
Dose	250 mg			250 mg			
Concentration	125 mg/mL			125 mg/mL			
Injection volumes	2 x 1 mL (2 mL total)			1 x 2 mL (2 mL total)			
Number of injections	2			1			
Injection duration	5 to 10 seconds per injection			Approximately 5 seconds			
Formulation and presentation	Solution in a PFS			Solution in an AI			

Abbreviations: AI = autoinjector; PFS = pre-filled syringe.

The PFSs and investigational AIs containing LY3074828 will be supplied fully assembled to the clinical site by Lilly.

Injections, whether administered by PFS or AI, will be given into the arm, thigh, or lower quadrant of the abdomen. For PFS administrations requiring 2 injections, subjects randomized to a group with the arm or thigh as the injection site will have both injections administered to the same limb (same arm or same thigh). Subjects randomized to the group with the abdomen as the injection site will have the 2 PFS injections administered to separate lower quadrants (right and left) of the abdomen. Investigational product will be administered to subjects on-site by designated trained clinical site personnel.

Prior to the PFS or AI injection, the investigator or his/her designee will prepare the subject's skin per Instructions for Use (IFU). Injections into the arm, thigh, or abdomen will be administered by investigative site staff according to the instructions provided by the sponsor. All study injection sites will be marked using a template for size and with a surgical marker in order to identify study injection sites for later assessments. Further information regarding SC administration will be included in the device IFU for the PFS and in the device IB (which contains IFU) for the AI.

In some cases, the site may destroy the material if, during the investigative site selection, the evaluator has verified and documented that the site has appropriate facilities and written procedures to dispose of clinical trial materials.

### **7.1.1. *Packaging and Labeling***

LY3074828 will be supplied by the sponsor or its designee in accordance with current good manufacturing process, and labeled according to the country's regulatory requirements. All IPs will be stored, inventoried, reconciled, and returned or destroyed according to applicable regulations. The following products will be supplied by Lilly:

- pre-assembled LY3074828 PFSs, 1 mL
- pre-assembled investigational LY3074828 AIs, 2 mL

Each investigational device will be individually identified and labeled according to US regulatory requirements for investigational devices.

## **7.2. *Method of Treatment Assignment***

Subjects will be randomized to a 2 x 1-mL PFS arm, thigh, or abdomen administration or a 1 x 2-mL AI arm, thigh, or abdomen administration ([Table AMAR.2](#)).

Randomization will be performed using a computer-generated randomization schedule.

### **7.2.1. *Selection and Timing of Doses***

The actual time of all dose administrations (including both the first and second of the 2 PFS injections) will be recorded in the subject's eCRF.

### 7.3. Blinding

This is an open-label study.

### 7.4. Dose Modification

Dose adjustments are not permitted in this study.

### 7.5. Preparation/Handling/Storage/Accountability

The IPs for this study will be:

- LY3074828 in PFSs
- LY3074828 in investigational AIs

Investigational product will be stored refrigerated at 2°C to 8°C (36°F to 46°F) in its original carton to protect from light. Investigational product should not be frozen or shaken. Sites will be required to monitor temperature of the on-site storage conditions of the IP. The investigator or designee must confirm appropriate temperature conditions have been maintained, as communicated by sponsor, during transit for all IP received and any discrepancies are reported and resolved before use of the study treatment.

The AIs and PFSs containing LY3074828 should be allowed to warm to room temperature before use.

Only participants enrolled in the study may receive IP or study materials, and only authorized site staff may supply or administer IP. All IP should be stored in an environmentally controlled and monitored (manual or automated) area in accordance with the labeled storage conditions with access limited to the investigator and authorized site staff.

The investigator is responsible for study treatment accountability, reconciliation, and record maintenance (such as receipt, reconciliation, and final disposition records).

### 7.6. Treatment Compliance

The IP will be administered at the clinical site, and documentation of treatment administration will occur at the site.

### 7.7. Concomitant Therapy

Over-the-counter or prescription medications, including herbal medication, are not permitted within 14 days prior to dosing and throughout the study. However, stable doses of oral contraceptive or hormone-replacement therapy are permitted at the discretion of the investigator.

Paracetamol/acetaminophen (up to 2 g/day) is permitted at the discretion of the investigator, but should be avoided during the 4-hour postdose period when pain assessments are made. Additional drugs are to be avoided during the study, unless required to treat an AE.

If the need for concomitant medication arises, inclusion or continuation of the subject may be at the discretion of the investigator after consultation with a Lilly clinical pharmacologist (CP) or clinical research physician (CRP). Any additional medication used during the course of the study must be documented.

## **7.8. Treatment after the End of the Study**

This section is not applicable for this study.

## 8. Discontinuation Criteria

### 8.1. Discontinuation from Study Treatment

Randomized subjects who discontinue the study prematurely for any reason should complete the early discontinuation (ED) procedures as shown in the Schedule of Activities (Section 2). The reason for, and the date of discontinuation, will be collected for all subjects.

#### 8.1.1. *Discontinuation of Inadvertently Enrolled Subjects*

If the sponsor or investigator identifies a subject who did not meet enrollment criteria and was inadvertently enrolled, a discussion must occur between the Lilly CP or CRP and the investigator to determine if the subject may continue in the study. If both agree it is medically appropriate to continue, the investigator must obtain documented approval from the Lilly CP or CRP to allow the inadvertently enrolled subject to continue in the study. Any subjects that are inadvertently enrolled will be followed for safety.

### 8.2. Discontinuation from the Study

Subjects will be discontinued in the following circumstances:

- Enrollment in any other clinical study involving an IP or enrollment in any other type of medical research judged not to be scientifically or medically compatible with this study
- Participation in the study needs to be stopped for medical, safety, regulatory, or other reasons consistent with applicable laws, regulations, and good clinical practice
- The investigator decides that the subject should be discontinued from the study
- The subject requests to be withdrawn from the study

Subjects who discontinue the study early will have ED procedures performed as shown in the Schedule of Activities (Section 2).

### 8.3. Subjects Lost to Follow-up

A subject will be considered lost to follow-up if he or she repeatedly fails to return for scheduled visits and is unable to be contacted by the study site. Site personnel are expected to make diligent attempts to contact subjects who fail to return for a scheduled visit or were otherwise unable to be followed up by the site.

## 9. Study Assessments and Procedures

Section 2 lists the Schedule of Activities, detailing the study procedures and their timing (including tolerance limits for timing).

[Appendix 2](#) lists the clinical laboratory tests that will be performed for this study.

[Appendix 5](#) provides a summary of the maximum number and volume of invasive samples, for all sampling, during the study.

The specifications in this protocol for the timings of safety and sample collection are given as targets to be achieved within reasonable limits. Modifications may be made to the time points based upon emerging clinical information. The scheduled time points may be subject to minor alterations; however, the actual time must be correctly recorded in the eCRF. Late collection outside the stipulated time allowances or failure to obtain samples due to clinical issues, such as problems with equipment, venous access, or subject defaulting on a scheduled procedure, will not be considered as protocol deviations but the site will still be required to notify the sponsor in writing via a file-note.

Unless otherwise stated in subsections below, all samples collected for specified laboratory tests will be destroyed within 60 days of receipt of confirmed test results. Certain samples may be retained for a longer period, if necessary, to comply with applicable laws, regulations, or laboratory certification standards.

### 9.1. Efficacy Assessments

This section is not applicable to this study.

### 9.2. Adverse Events

Investigators are responsible for monitoring the safety of subjects who have entered this study and for alerting Lilly or its designee to any event that seems unusual, even if this event may be considered an unanticipated benefit to the subject.

The investigator is responsible for the appropriate medical care of subjects during the study.

Investigators must document their review of each laboratory safety report.

The investigator remains responsible for following, through an appropriate health care option, AEs that are serious or otherwise medically important, considered related to the IP or the study. The subject should be followed until the event resolves, stabilizes with appropriate diagnostic evaluation, or is reasonably explained. The frequency of follow-up evaluations of the AE is left to the discretion of the investigator.

After the informed consent form is signed, study site personnel will record, via eCRF, the occurrence and nature of each subject's preexisting conditions. Additionally, site personnel will record any change in the condition(s) and the occurrence and nature of any AEs.

The investigator will interpret and document whether or not an AE has a reasonable possibility of being related to study treatment, study device, or a study procedure, taking into account concomitant treatment or pathologies.

A “reasonable possibility” means that there is a cause and effect relationship between the IP, study device, and/or study procedure and the AE.

Planned surgeries should not be reported as AEs unless the underlying medical condition has worsened during the course of the study.

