### **9.2.1. Serious Adverse Events**

An SAE is any AE from this study that results in one of the following:

- death
- initial or prolonged inpatient hospitalization
- a life-threatening experience (that is, immediate risk of dying)
- persistent or significant disability/incapacity
- congenital anomaly/birth defect
- important medical events that may not be immediately life-threatening or result in death or hospitalization but may jeopardize the patient or may require intervention to prevent one of the other outcomes listed in the definition above
- when a condition related to the investigational device (PFS or AI) necessitates medical or surgical intervention to preclude either permanent impairment of a body function or permanent damage to a body structure, the serious outcome of “required intervention” will be assigned.

Study site personnel must alert the Lilly CRP/CP, or its designee, of any SAE as soon as practically possible.

Additionally, study site personnel must alert Lilly Global Patient Safety (GPS), or its designee, of any SAE within 24 hours of investigator awareness of the event via a sponsor-approved method. If alerts are issued via telephone, they are to be immediately followed with official notification on study-specific SAE forms. This 24-hour notification requirement refers to the initial SAE information and all follow-up SAE information.

Although all AEs are recorded in the eCRF after signing informed consent, SAE reporting to the sponsor begins after the subject has signed informed consent and has received IP. However, if an SAE occurs after signing informed consent, but prior to receiving IP, AND is considered Reasonably Possibly Related to a study procedure then it MUST be reported.

Investigators are not obligated to actively seek AEs or SAEs in subjects once they have discontinued from and/or completed the study (the subject summary eCRF has been completed). However, if the investigator learns of any SAE, including a death, at any time after a subject has

been discharged from the study, and he/she considers the event reasonably possibly related to the study treatment or study participation, the investigator must promptly notify Lilly.

Pregnancy (maternal or paternal exposure to IP) does not meet the definition of an AE. However, to fulfill regulatory requirements any pregnancy should be reported following the SAE process to collect data on the outcome for both mother and fetus.

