#### **9.2.1.3. Suspected Unexpected Serious Adverse Reactions**

Suspected unexpected serious adverse reactions (SUSARs) are serious events that are not listed in the IB and that the investigator reports as related to IP or procedure. Lilly has procedures that will be followed for the recording and expedited reporting of SUSARs that are consistent with global regulations and the associated detailed guidances.

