8.4 Safety and Tolerability Assessments

8.4.1 Adverse events

Where changes in severity are recorded in the Case Report Form (CRF), each separate severity of the AE will be reported in the listings, only the most severe will be used in the summary tables. A pre-existing condition is defined as an AE that starts before the subject has provided written informed consent and is ongoing at consent. A non-treatment emergent AE is defined as an AE which starts after informed consent but prior to dosing. A treatment-emergent AE is defined as an AE which occurs postdose or which is present prior to dosing and becomes more severe postdose.

All AEs and product complaints will be listed. Treatment-emergent AEs will be summarized by treatment, severity and relationship to the study drug. The frequency (the number of AEs, the number of subjects experiencing an AE and the percentage of subjects experiencing an AE) of treatment-emergent AEs will be summarized by treatment, Medical Dictionary for Regulatory Activities (MedDRA) version 20.1 system organ class and preferred term. The summary and frequency AE tables will be presented for all causalities and those considered related to the study drug. Any serious AEs will be listed. Pre-existing conditions and medical history data will also be listed.

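### Protocol Section 9.2 asks for a judgement of possible relatedness, then defines that possibility as an existing cause-and-effect relationship; the two sentences conflict and need reconciling

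*Protocol*

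**What the plan says.** Protocol Section 9.2 (Adverse Events) sets the causality question. For each AE the investigator is to judge "whether or not an AE has a reasonable possibility of being related to study treatment, study device, or a study procedure", allowing for concomitant treatment and pathologies. The next sentence defines the key term: a reasonable possibility "means that there is a cause and effect relationship between the IP, study device, and/or study procedure and the AE".

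Other parts of the plan then use a relatedness judgement:

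- **Protocol 9.2.1, before dosing.** An SAE after consent but before the investigational product is given must go to the sponsor on a condition: it "is considered Reasonably Possibly Related to a study procedure then it MUST be reported".
- **Protocol 9.2.1, after discharge.** Sites need not actively seek events once a subject has left the study. An investigator who learns of an SAE must notify the sponsor if "he/she considers the event reasonably possibly related to the study treatment or study participation".
- **Protocol 9.2.1.3.** SUSARs are "serious events that are not listed in the IB and that the investigator reports as related to IP or procedure".
- **Protocol 9.2.** The continuing duty to follow serious or medically important AEs is tied to those judged related to the product or the study.
- **Protocol 10.3.1.1 and SAP 8.4.1.** Protocol summaries are split by the association with product that the investigator perceives. The SAP presents AE tables for all causalities and again for "those considered related to the study drug".

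**The concern.** The question is about possibility, and the definition is about fact. An event can have a plausible link to the injection without anyone being able to say that the link exists. Such an event satisfies the question and fails the definition. An investigator who looks up the term finds only this one sentence, because neither document gives another definition of relatedness.

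The stake is safety notification and classification. Before dosing and after discharge, the judgement decides whether the sponsor is notified of an SAE at all. On study, it decides whether an unlisted serious event counts as a SUSAR. It also decides which events enter the related-AE tables.

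**Working it through.** No figure in the plan bears on this point, so the check is of the text. It has three steps.

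**1. Compare the two sentences in Section 9.2.**

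| | Question | Definition |
|---|---|---|
| What is asserted | A reasonable possibility of being related | A cause-and-effect relationship exists |
| Qualifier | Possibility | None (no may, suspected or evidence to suggest) |
| Plausible but unconfirmed event | Related | Not related, if read literally |

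The last row shows that the sentences can give opposite answers for the same event.

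**2. Look for another definition.** The abbreviations and definitions in Protocol Appendix 1 define an AE and a TEAE and say that neither requires a causal relationship, but they do not define relatedness. SAP 8.4.1 defines pre-existing, non-treatment-emergent and treatment-emergent events, and again not relatedness. Section 9.2 is therefore the only source.

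**3. Trace each use and ask whether the definition reaches it.**

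| Use | Does relatedness decide it? | Reached by the definition? |
|---|---|---|
| SAE before dosing: notify sponsor (9.2.1) | Yes | Yes, by inference |
| SAE learned of after discharge: notify sponsor (9.2.1) | Yes | Yes, by inference |
| SUSAR classification (9.2.1.3) | Yes | Yes, by inference |
| Follow-up of serious or medically important AEs (9.2) | Yes | Yes, by inference, within the same section |
| Summaries by relation to product (10.3.1.1; SAP 8.4.1) | Yes | Yes, by inference |
| Recording of AEs after consent (9.2; 9.2.1) | No | No |
| SAE on study after dosing: report within 24 hours (9.2.1) | No | No |
| Adverse device event (9.2.1.1) | Yes, but on the site's belief that the event relates to a device issue | No, it has its own trigger |
| Primary safety endpoint, incidence of TEAEs (Section 4) | No | No |

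The entries marked as inference are so marked because those sections use neighbouring wording and do not repeat the exact defined phrase. The inference is sound: the pre-dose and post-discharge triggers use the adverbial form of the same term, and there is no rival definition.

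**The case against.** The strongest reply is that the definition says what kind of relation is being judged (causal, and not merely temporal) and not how certain the investigator must be. On that reading the preceding sentence still sets the threshold. The later triggers support it, since they speak of what the investigator considers, believes or perceives, and none repeats the cause-and-effect wording. Experienced investigators may well read it this way. That stands as a reason not to claim that events will be lost. It does not remove the defect, because the sentence as written carries no such limitation and a definition should not depend on being read generously.

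The safeguards are also real. All AEs after consent are recorded, including those before dosing. Sites must alert the sponsor to anything that seems unusual. SAEs on study after dosing reach the sponsor within 24 hours whatever their cause. SUSAR reporting follows sponsor procedures that are not in these documents. These narrow the exposure, but they leave the written conditions in the first five rows of the tracing table unchanged.

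Four stronger readings are tempting, and the documents do not support them:

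- **That causality must be proven or established.** The text says that a relationship exists. It sets no standard of proof.
- **That drug, device and procedure attributions are equally affected.** The definition names all three, but Section 9.2.1.1 gives adverse device events a separate trigger based on belief.
- **That the definition biases the comparison of autoinjector with pre-filled syringe because the study is open-label.** Differential attribution comes from the lack of blinding and is possible under any threshold. Nothing in the documents shows that a stricter one makes it worse. The SAP's related tables concern relation to the drug, which is the same drug at the same 250-mg dose in all six arms.
- **That the related-AE count falls by some stated fraction.** The documents give no information on how many events would be plausible but unconfirmed, so any such fraction would only restate an assumption.

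**Conclusion.** The point holds as an internal contradiction in the written threshold for relatedness. Read literally, the definition screens out events whose causal link is possible but unconfirmed. It does so for notification of SAEs before dosing and after discharge, SUSAR classification, follow-up of serious or medically important related AEs, and the related-AE summaries.

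No primary analysis changes: the TEAE endpoint is all-causality, and the PK and pain endpoints do not use relatedness. The number of events affected, among about 66 subjects given a single dose, cannot be estimated from the documents. The conclusion rests on two assumptions: that Section 9.2 governs relatedness wherever it is used without its own trigger, and that some readers would apply the definition as written. The documents support the first by offering no alternative. They are silent on the second.

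**What to change.** Reword the one sentence in Protocol Section 9.2 so that it matches the term it defines. For example: a reasonable possibility means there is reason to suspect that the investigational product, study device and/or study procedure may have caused or contributed to the AE; causality need not be confirmed.

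No change to the SAP tables is needed, since they take the investigator's classification as given. If sites have separate instructions on causality, which are not among the documents, these should be checked against the new sentence.

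The cost is one sentence in a protocol amendment. The downside is that slightly more events may be classed as related.
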